5.2.5.3 Exploratory efficacy analyses

For all exploratory efficacy endpoints, the analyses will be based on observed data only *i.e.*, no data will be imputed.

EO1: To evaluate the efficacy and estimate the size of effect of PRM-151 relative to placebo in change from baseline to weeks 4, 8, 12, 16, 20, and 24 in FVC % predicted, FVC in ml and 6 minute walking distance, pooling subjects on a stable dose of pirfenidone or nintedanib with subjects not on other treatment for IPF and separately in subjects on a stable dose of pirfenidone or nintedanib and in subjects not on other treatments for IPF.

A model similar to that of the primary analysis (see section 5.2.5.1) but with the addition of random slopes will be used to evaluate on both the ATS and the PP data sets the efficacy and estimate, pooling subjects on a stable dose of pirfenidone or nintedanib with subjects not on other treatment for IPF and separately in subjects on a stable dose of pirfenidone or nintedanib and in subjects not on other treatments for IPF, the size of effect of PRM-151 relative to placebo in time variations in FVC [% predicted] (Statistical tables 14.2.13.1 to 14.2.14.2.2, Figures 14.2.10.1 to 14.2.11.2.2), FVC [ml] (Statistical tables 14.2.15.1 to 14.2.16.2.2, Figures 14.2.12.1 to 14.2.13.2.2) and 6MWD (Statistical tables 14.2.17.1 to 14.18.2.2, Figures 14.2.14.1 to 14.2.15.2.2). The individual slopes and intercepts will be listed (Listings 16.2.6.10 to 16.2.6.12). Statistical inference (90% CI and p-values) on the slope difference between treated and placebo groups will be reported.

EO2: To assess the impact of PRM-151 on disease related symptoms and quantitative imaging.

Mean change from Baseline to Week 28 in total lung volume and volume of parenchymal features (see section 8) on HRCT (in ml and % of total lung volume), representative of interstitial lung abnormalities (ILA) will be computed, comparing PRM151 vs. placebo (separately) in patients with SVC breathhold at CT scanning $\geq 90\%$ of SVC supine, with a similar approach to the one used

for the primary analysis (statistical tables 14.2.19.1.1.1 to 14.2.19.2.3.2, Figure 14.2.16.1.1 to 14.2.16.2.2).

For all categories of lung features (including PVV), the change from baseline to week 28 in volume of a given lung feature (both in ml as well as in % of total lung volume) will be computed in subjects treated with PRM-151 and placebo, depending on the completeness and usability of the obtained data.

Change in Patient Reported Outcomes will be assessed based on the King's Brief Interstitial Lung Disease Questionnaire (K-BILD) and Leicester Cough Questionnaire (LCQ). Descriptive statistics for raw values and change from Baseline to each visit in total score of both questionnaire will be computed by treatment group. Differences between treatment groups in change from baseline to week 28 for total score of each questionnaire will be tested using a similar approach to the one used for the primary analysis (see section 5.2.5.1). These analysis will be performed on both the ATS and the PP data sets (Statistical tables 14.2.20.1.1 to 14.2.20.3.2 and 14.2.21.1.1 to 14.2.21.3.2, Figures 14.2.17.1 to 14.2.17.2 and 14.2.18.1 to 14.2.18.2). All results of K-BILD and LCQ will be reported in Listings 16.2.6.4.1 to 14.2.6.4.2.2 and 16.2.6.5.1 to 16.2.6.5.2.2.

For the LCQ, in addition to the above approach, frequency of patients with changes below or above 1.3 (identified as the minimal important difference) will be tabulated by treatment groups at week 4, 8, 12, 16, 20, 24 and 28 (Statistical table 14.2.21.4.1 and 14.2.21.4.2).

Descriptive statistics for raw values at each visit and change from baseline to each visit in anti-Pentraxin-2 antibodies measurements will be computed by treatment group. This analysis will be performed on both the ATS and the PP dataset (Statistical 14.2.22.1.1 to 14.2.22.2.2). Individual measurements of anti-pentraxin-2 antibodies will be reported in Listing 16.2.6.8.

EO3: To assess the use of quantitative imaging in IPF

The correlation between baseline FVC [% predicted], DLCO (corrected for Hb, [% predicted]), TLC by nitrogen washout, PROs and 6MWD and total lung volume and volume of parenchymal features on HRCT (in ml and % of total lung volume) representative of ILA by quantitative imaging, as well as change from Baseline to Week 28 in FVC [% predicted], DLCO (corrected for Hb, [% predicted]), TLC by nitrogen washout, PROs and 6MWD and change from Baseline to Week 28 in total lung volume and volume of parenchymal features on HRCT (in ml and % of total lung volume) representative of ILA will be computed. This analysis will be performed on both the ATS and the PP dataset (Statistical tables 14.2.23.1.1 to 14.2.23.1.2).

For all categories of lung features (including PVV) the correlation between (i) change from baseline to week 28 in volume of a given lung feature (both in ml as well as in % of total lung volume) and (ii) change from baseline to week 28 in FVC [% predicted] will be computed. This analysis will be performed on both the ATS and the PP dataset (Statistical tables 14.2.23.2.1 to 14.2.23.2.2).

For all categories of lung features (including PVV) the correlation between (i) change from baseline to week 28 in volume of a given lung feature (both in ml as well as in % of total lung volume) and (ii) change from baseline to week 28 in DLCO will be computed. This analysis will be performed on both the ATS and the PP datasets (Statistical table 14.2.23.3.1 to 14.2.23.3.2).

The impact of inspiratory effort on results of HRCT quantitative imaging will be assessed by (Statistical table 14.2.23.4.1 to 14.2.23.4.2, Figure 14.2.19.1 to 14.2.19.2):

1. Calculating the proportion of patients performing spirometry guided HRCT with a SVC breathhold at CT scanning $\geq 90\%$ of SVC supine at baseline and at week 28
2. The correlation of SVC breathhold at CT scanning and SVC supine at baseline and at week 28
3. The correlation between (i) baseline Total lung volume by quantitative imaging and (ii) baseline TLC by nitrogen washout, separately for patients with SVC breathhold at CT scanning $\geq 90\%$ of SVC supine, and for patients with SVC $< 90\%$ or not receiving spirometry-guided HRCT.

EO4: To assess the impact of PRM-151, disease pathogenesis and disease progression on exploratory serum, cellular and genetic biomarkers

To assess the impact of PRM-151 on exploratory biomarkers, descriptive statistics for change from baseline to week 28 in biomarkers will be computed by treatment group and by baseline genetic status (MUC5B and TLR polymorphism separately). These analyses will be performed on both the ATS and the PP dataset (Statistical table 14.2.24.1 and 14.2.24.2). Individual biomarker values will be reported in Listing 16.2.6.6. All or part of these analyses may be provided at a later stage than the rest of the analyses described in the SAP, might the corresponding data not be available at the time of the database lock. It is currently anticipated that baseline genetic status will be available, but biomarkers will not.

Additional exploratory analysis: ADA vs. FVC [% predicted]

The relationship between Anti-Pentraxin 2 antibodies (ADA) presence and level of FVC [% predicted] in time will be studied by modelling the influence of presence/absence (and/or level) of ADA in the repeated measures mixed model used for the primary efficacy analysis (see section 5.2.5.1) and if relevant using non-parametric spline functions. The most parsimonious model will be chosen on the basis of the AIC (Statistical table 14.2.25.1 and 14.2.25.2).

Additional exploratory analysis: Baseline characteristics vs. FVC

If data lend themselves to it, additional exploratory analysis will be done to test for interaction between baseline characteristics (e.g., FVC/DLCO/6MWD) and change in FVC.

Exploratory analysis of PK/PD relationship

Descriptive statistics and correlation will be computed to explore the relationship of Pentraxin-2 levels vs FVC [% predicted]/FVC [ml]/slope of FVC ml at week 24 and 28, and the relationship of

Pentraxin-2 vs other PFTs/PROs/6MWT (Statistical table 14.2.26.1 and 14.2.26.2). If relevant the corresponding scatter plot will be produced.

Exploratory analysis of relationship between Pentraxin-2 levels and ADA

Correlation coefficient between Pentraxin-2 levels and ADA titer at week 28 will be computed (Statistical tables 14.2.27.1 and 14.2.27.2) and a scatterplot prepared (using logarithmic coordinates for titers).

Exploratory analysis of acute exacerbations

Tabulation of each type of acute exacerbations will be produced (Statistical table 14.2.28.1.1 and 14.2.28.1.2). Descriptive statistic and Kaplan-meier curve will be computed by treatment group for time to first reported acute exacerbation (Statistical tables 14.2.28.2.1 and 14.2.28.2.2).

Additional exploratory analysis: FVC [% predicted] separately on pirfenidone and nintedanib

The same model as the one for the primary analysis (see section 5.2.5.1) will be used separately on (i) patient on a stable dose pirfenidone and (ii) patient on a stable dose of nintedanib (Statistical table 14.2.20.1.1 to 14.2.20.2.2).

Additional exploratory analysis: time variation in historic FVC [% predicted; ml] measurements:

The time variations in historic FVC [% predicted] data (see section 8) will be modelled using a linear mixed effect model with random intercept and slope, with available historic FVC measurements for each patient (until baseline, baseline included) as dependent variable (outcome) and time (continuous variable calculated as the actual number of days before baseline) as explanatory variables (Statistical table 14.2.30.1.1 to 14.2.30.1.2, Figure 14.2.21.1.1 to 14.2.21.1.2). This analysis will be repeated using historic FVC [ml] measurement as dependent variable. (Statistical table 14.2.30.2.1 to 14.2.30.2.2, Figure 14.2.21.2.1 to 14.2.21.2.2). All available individual measurements will be provided in Listing 16.2.6.13.

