The per-protocol set will be used for secondary analyses of the primary efficacy criterion and for the analysis of some selected secondary efficacy criteria. Safety evaluations will be based on the Safety Population, defined as all subjects who receive at least 1 dose of study drug and have a post-Baseline safety observation. Demographic data will be summarized for all subjects entering the study, and if material differences exist, for the FAS and Safety analysis datasets. (Additional details will be included in the SAP.)

This study is randomized with a 2:1 randomization ratio. A central randomization system will be used. The randomization will be stratified according to the subject's baseline treatment status: baseline pirfenidone or baseline nintedanib or no other therapy for IPF at baseline. The randomization system will also ensure that at least 25% of the subjects in the final study population are on no other therapy for IPF at baseline.

The comparison of PRM-151 with placebo will be carried out via 2-sided statistical tests at alpha=0.10. The primary endpoint will be tested with analysis of variance (ANOVA), with change from Baseline to week 28 in FVC% predicted as dependent variable (outcome), and treatment and stratum, as explanatory variables. FVC% predicted will also be analyzed separately for each level of the stratum variable (in subjects on a stable dose of pirfenidone or nintedanib and in subjects not on other treatments for IPF) using analysis of variance

(ANOVA), with change from Baseline to week 28 in FVC% predicted as dependent variable (outcome), and treatment as the explanatory variable. In case of missing Week 28 assessment of FVC% predicted, the last available observation will be carried forward.

A similar analysis will be done for the secondary and exploratory endpoints, replacing FVC % predicted with the other endpoints as appropriate. Analyses over time will use a three-way ANCOVA with time (nominal study week) as the third factor, including all interactions. The analysis will adjust for correlated errors over time.

For all secondary and exploratory efficacy endpoints, the analyses will be based on observed data only; no data will be imputed.

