The ANOVA model described above (see Section 8.5.1.1) for the primary efficacy analysis will be used for the analysis of the primary efficacy endpoint on the PP analysis set.

8.5.1.3. Secondary efficacy analyses:*8.5.1.3.1. Analyses of quantitative secondary and exploratory efficacy endpoints:*

A similar analysis as described for the primary endpoint in Section 8.5.1.1 will be done for the secondary and exploratory efficacy variables, replacing FVC % predicted with the other variables as appropriate. These analyses will be conducted on the FAS and Per Protocol set.

FVC% predicted will also be analysed separately for each level of the stratum variable (in subjects on a stable dose of pirfenidone or nintedanib and in subjects not on other treatments for IPF) using analysis of variance (ANOVA), with change from Baseline to week 28 in FVC% predicted as dependent variable (outcome), and treatment as the explanatory variable.

8.5.1.3.2. Analyses of quantitative primary, secondary and exploratory efficacy endpoints evolution over time:

The evolution of each efficacy variable with time will be compared between the two groups using a likelihood-based Mixed effects Model for Repeated Measures (MMRM) including treatment, stratum and time as fixed factors, the time by treatment interaction, the baseline (Day 1) measurement as covariate and the subject effect as a random effect to adjust for correlated errors over time. This analysis will be conducted on the FAS for all secondary and exploratory efficacy endpoints and on both the FAS and PP set for FVC % predicted.

8.5.1.3.3. *Analyses of categorical secondary and exploratory efficacy endpoints:*

Percentages of subjects in each category will be computed per treatment group.

The two treatment groups will be compared using a stratified statistical test (Cochran-Mantel-Haenszel general association test in SAS Freq procedure), adjusting for the Stratum effect. If the assumptions underlying the use of the asymptotic test are not met, the exact version of the test will be used.

8.5.2. **Safety Analyses**

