5.2.5 Efficacy Analysis

5.2.5.1 Primary endpoint analysis

Primary efficacy analysis

Descriptive statistics for (i) raw values at each time point and (ii) change from baseline to each time point in FVC [% predicted] will be computed by treatment group for the ATS analysis dataset (Statistical tables 14.2.1.1.1 and 14.2.1.2.1). The time variation in FVC [% predicted] will be modelled using a linear mixed effect model with random intercept, with raw values at each time point (from Week 4 to Week 28 included) in FVC [% predicted] as dependent variable (outcome), and stratum, treatment, time (continuous variable calculated as the actual number of days since baseline) and treatment by time interaction as explanatory variables (Statistical table 14.2.1.3.1).

The following statistical hypotheses will be tested:

- H0: Absence of difference between the treatment groups.
- H1: A difference exists between the treatment groups.

Least square means for FVC [% predicted] at each time-point (Statistical table 14.2.1.3.1, Figure 14.2.1.1), estimate of slopes, together with their 2-sided 90 and 95% confidence intervals will be presented for both treatment groups.

The comparison of PRM-151 with placebo will be carried out by

1. computing the estimate (estimate statement from SAS Proc MIXED) of the between group difference in change from baseline at week 28,
2. computing the corresponding 90% confidence interval
3. computing the p-value of the difference estimate compared to 0.

Statistical significance will be determined using a 2-sided type-one error rate of 0.10.

The listing of the estimates of the random parameters will be provided (Listing 16.2.6.9.1)

Due to the number of sites planned to recruit and randomize patients in the study, it is expected that each site will include too few patients to allow the inclusion of study site as a covariate in the analysis.

Sensitivity efficacy analysis on the Full Analysis Set population

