6.3 Changes in exploratory efficacy analyses

All exploratory efficacy analysis will be performed on both the ATS and the PP.

It was initially planned (EO1) to evaluate the efficacy and estimate the size of effect of PRM-151 relative to placebo in change from baseline to weeks 4, 8, 12, 16, 20, and 24 in FVC % predicted, FVC in ml and 6 minute walking distance using mixed models with random intercepts. To obtain a better description of individual variability, both random intercepts and random slopes will be used.

The following not initially planned exploratory analysis were added (see section 5.2.5.3 for details):

- To assess the use of quantitative imaging in IPF (E03)
- To explore the relationship between Anti-Pentraxin 2 antibodies (ADA) presence and level of FVC [% predicted] in time
- To explore PK/PD relationship.
- To explore relationship between Pentraxin-2 levels and ADA
- To explore acute exacerbations
- To explore time variations in FVC % predicted separately in patient (i) on stable dose of pirfenidone and (ii) on a stable dose of pirfenidone.

7 Software documentation

All summaries and statistical analyses will be generated using SAS version 9.4 or higher.

8 Derived data

Derived variable	Derivation algorithm
Change from baseline to visit V (continuous)	Change from baseline of variable $X = X_{(Visit V)} - X_{(Baseline)}$ 
 ○ Negative values indicate a decrease in X ○ Positive values indicate an increase in X

Percent change from baseline to visit V (continuous)	Percent change from baseline of variable X= $100 * [X_{(Visit V)} - X_{(Baseline)}] / X_{(Baseline)}$ 
 ○ Negative values indicate a decrease in X ○ Positive values indicate an increase in X
Treatment compliance	Continuous variable: The compliance C_i for patient i will be computed according to: $C_i = \frac{D_i^t * 100}{D_i^p}$ 
where D_i^p mg is the total amount (mg) of IP prescribed to patient i and D_i^t is the total amount (mg) of IP actually taken by the patient during the study i.e., before the end of study for patient i.

Treatment compliance (categorical)	Categorical variable with three modalities: 
 • $C_i < 80\%$ • $80\% \leq C_i < 120\%$ • $C_i \geq 120\%$

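### EO1 asks for the treatment effect at each of Weeks 4 to 24, but its default model fits one straight line per arm and commits only to inference on the slope difference

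*SAP*

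**What the plan says.** **Objective.** SAP 5.2.5.3 (EO1) wants the size of effect "in change from baseline to weeks 4, 8, 12, 16, 20, and 24 in FVC % predicted, FVC in ml and 6 minute walking distance", pooled and separately by background-therapy stratum.

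**Model.** The same paragraph states: "A model similar to that of the primary analysis (see section 5.2.5.1) but with the addition of random slopes will be used". The primary model in SAP 5.2.5.1 is fitted "with raw values at each time point (from Week 4 to Week 28 included) in FVC [% predicted] as dependent variable", with stratum, treatment, "time (continuous variable calculated as the actual number of days since baseline) and treatment by time interaction as explanatory variables".

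**Inference.** The only inference that EO1 names is: "Statistical inference (90% CI and p-values) on the slope difference between treated and placebo groups will be reported". SAP 9.1 lists least-squares means for change at each visit from the random-slope model, but these are read off the fitted lines.

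**Protocol.** Section 8.5.1.3.2 plans a likelihood-based repeated-measures model "including treatment, stratum and time as fixed factors, the time by treatment interaction, the baseline (Day 1) measurement as covariate", with subject as a random effect. The synopsis says: "Analyses over time will use a three-way ANCOVA with time (nominal study week) as the third factor, including all interactions". The two differ on which interactions enter, but both treat time as a factor.

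**Listed change.** SAP 6.3 describes the plan being replaced as mixed models with random intercepts and gives one change: "To obtain a better description of individual variability, both random intercepts and random slopes will be used". It does not mention the move from factor to linear time.

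**Related provisions.** SAP 5.1.2 makes time continuous in all models and provides a refit with categorical time if residuals suggest a departure from assumptions. SAP 5.3.1 says that pooled mixed models adjust for the baseline value, which is not among the terms listed in 5.2.5.1.

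**The concern.** The objective concerns six separate time points, while the committed analysis yields one number per endpoint, a difference in slopes. Random slopes change the covariance structure only, so each arm's mean stays a straight line. Onset and durability of effect are what a week-by-week objective is for, and a line cannot show a rise followed by a plateau.

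An early gain is not far-fetched. Protocol Section 1.2 reports a mean change in FVC % predicted of +2.4 on PRM-151 against -1.5 on placebo at Day 57 in the previous IPF study.

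The reason given in SAP 5.1.2 for continuous time, that missing values are not imputed, does not require it. The protocol's likelihood-based model with time as a factor also uses observed data only.

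**Working it through.** **1. The plan's own figure.** The documents give no figure for EO1. The sample size supplies a scale. Taking the stated stratum means as the placebo values, the placebo mean is 0.75 × (-1.5) + 0.25 × (-3) = -1.875, and the difference is 0.75 + 1.875 = 2.625. With SD 5, two-sided alpha 0.10, power 80% and 2:1 allocation, placebo n = 1.5 × (1.645 + 0.842)² × 25 / 2.625² = 33.7, so 34 + 68 = 102 (power 80.4%). This reproduces the stated size. The point below does not depend on it.

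**2. What the model allows.** Let A be treatment (0/1) and t time. The fixed part is: intercept + stratum + b·A + g·t + d·A·t. SAP 5.2.5.1 mentions an estimate statement but gives no coefficients, so two readings are open.

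- *Interaction only.* With the terms in 5.2.5.1, change can be taken as fitted(t) minus fitted(0). The arm difference is D(t) = d·t and its SE is t·SE(d). The ratio is d/SE(d) at every t, so there is one p-value, and Week 4 is 4/28 = 14.3% of Week 28. A Week 28 effect of 2.625 forces 0.375, 0.75, 1.125, 1.5, 1.875 and 2.25 at Weeks 4 to 24.
- *Treatment term kept.* With baseline as a covariate (5.3.1), D(t) = b + d·t. This is not proportional to t and its p-value varies with t. It is still two parameters for seven visits.

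SAP 5.3.1 speaks of pooled models. For the separate-stratum fits it does not say whether baseline is included.

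**3. Illustration without sampling error.** Assume a true difference of 2.625 × (1 - exp(-t/3)), t in weeks, and complete data at Weeks 4 to 28. The least-squares line has b = 2.136 and d = 0.0222 per week.

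| Week | 4 | 8 | 12 | 16 | 20 | 24 | 28 |
|---|---|---|---|---|---|---|---|
| Assumed truth | 1.93 | 2.44 | 2.58 | 2.61 | 2.62 | 2.62 | 2.62 |
| b + d·t | 2.22 | 2.31 | 2.40 | 2.49 | 2.58 | 2.67 | 2.76 |
| d·t | 0.09 | 0.18 | 0.27 | 0.35 | 0.44 | 0.53 | 0.62 |

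The line with the treatment term is off by at most 0.29 (Week 4) but shows a steady rise where the truth is flat. The interaction alone loses most of the effect, because the early gain sits in b.

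**4. One simulated dataset.** This had 102 patients, assumed variances, and a true effect of 1.312 at Week 4 and 2.625 from Week 8.

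- Interaction only: -0.005 (SE 0.103) at Week 4 and -0.033 (SE 0.720) at Week 28, p = 0.963 throughout.
- Treatment term kept, baseline-adjusted: 2.25 at Week 4 (p < 0.0001), 2.23 at Week 24 (p = 0.0007), 2.22 at Week 28 (p = 0.0022).
- Time categorical: 1.87, 2.40, 2.58, 2.35, 1.87 and 2.43 at Weeks 4 to 24, p from 0.0002 to 0.007.

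**5. Would the residual check trigger the refit?** In step 3 the largest misfit in the arm difference is 0.29 points. The only SD in the documents is 5, for change at Week 28, and 0.29/5 = 0.06. The within-patient residual SD is not given, so the comparison is rough, but a misfit of this size could easily pass a graphical check. The residuals are the same whichever contrast is then taken, so they give no warning about the interaction-only reading. The refit also names eight time levels, whereas the outcome has seven visits.

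**The case against.** **A constant p-value is not established.** A reader might infer that every weekly effect must be the slope difference rescaled, with Week 4 always 14% of Week 28. That needs the interaction-only contrast. The SAP gives no coefficients, the outcome starts at Week 4, and 5.3.1 puts baseline into the pooled models. Under that reading it is natural to keep the treatment term, and the fitted weekly effects in step 3 are then close to the assumed truth. This objection stands: the large loss in the last row of the table comes from dropping the treatment term, not from linear time itself.

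**The time course is not wholly out of reach.** A reader might also infer that it cannot be estimated at all. Change from baseline by visit and arm is tabulated for FVC % predicted, FVC in ml and walk distance, and 5.1.2 prespecifies a categorical-time refit for non-linear trend. Both provisions are real. However, the tables carry no between-arm inference, although 5.1.2 promises 90% CIs for exploratory endpoints, and the refit hangs on a judgement about plots.

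**The evidence for an early plateau is thin.** The Day 57 result is one time point in 14 against 6 patients on a different dosing schedule. It makes an early gain plausible but says nothing about a plateau.

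**EO1 is exploratory,** with no multiplicity control, and 5.1.2 states continuous time openly. This limits the weight of the point but does not explain the omission from 6.3.

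**Conclusion.** The point holds in a limited form. By default EO1 fits one straight line per arm and commits to inference on the slope difference, so it provides no between-arm estimate at each week that is free of the linearity assumption. That matches neither the objective nor the protocol's time-as-factor model, and SAP 6.3 does not record the change.

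The size cannot be fixed from the documents. For the plateau assumed in step 3, the error at any week is at most 0.29 points if the treatment term is kept. With the interaction alone, 0.62 is reported at Week 28 against 2.62. The plateau shape and the simulation variances are assumptions used only for illustration. The documents do not support saying that all weeks must share a p-value, or that no information by week will exist. The change is worth making, at moderate priority, in an exploratory analysis.

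**What to change.** For EO1, prespecify the model of protocol 8.5.1.3.2: visit (Weeks 4 to 28) as a seven-level factor, treatment by visit, stratum in the pooled analysis, and baseline value. Report the between-arm difference with 90% CI at each visit for FVC % predicted, FVC in ml and 6-minute walk distance. Keep the random-slope model as the summary of rate of decline, and list the move between factor and linear time in SAP 6.3.

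For the covariance, use the protocol's random subject effect. Alternatively, use an unstructured matrix in the pooled analysis with a prespecified simpler fallback. The protocol section does not specify an unstructured matrix, and it would be fragile by stratum: 7 × 8 / 2 = 28 parameters, against about 0.25 × 117 = 29 patients without background therapy, about 10 of them on placebo.

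The cost is SAP wording and up to 3 endpoints × 3 populations (pooled and two strata) × 2 analysis sets = 18 further fits. Intervals at single visits will tend to be somewhat wider. In the simulated dataset the categorical SE was 0.69, against 0.50 to 0.66 for the baseline-adjusted line at Weeks 4 to 24.
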